2.2 Subjects and Sites

We will work with [name] team and select Mental Health Institute of Second Xiangya Hospital that has approved for carrying out CNS drug registration trial by China Food and Drug Administration and well experienced in doing the MDD trial in China. A total of 120 patients with MDD will be enrolled and randomly divided into 2 groups. Sixty subjects will be given fish oil and another 60 subjects given placebo (control group). We plan to enroll all 120 patients in 12 months and each patient will be on study medication (or placebo) for 24 weeks and then be followed up for after 24 weeks (the follow-up period will be last for 48 weeks). We plan to have this trial done in two year period.

Participants

Inclusion criteria:

- ① Able to provide informed consent;
- ② Men or women aged 18-50 years;
- ③ A primary psychiatric diagnosis of major depressive disorder (MDD), by Diagnostic and Statistical Manual-5th ed (DSM-5) using the MINI;
- ④ HAMD total score ≥ 21 ;
- ⑤ No significantly modification of their diet from the time they sign consent to the end of study participation.

Exclusion criteria:

- ① Suffering from other serious somatic diseases or comorbidities;

- ②Patients with serious nervous system disease;
- ③Patients in accordance with diagnostic standards of other mental illness;
- ④ Patients who need to take benzodiazepine every day, and who currently need to be treated by electroconvulsive therapy or have received electroconvulsive therapy in the past 6 months;
- ⑤Pregnant women or lactating women, women with pregnancy plans during the trial period (12 months), women with a high risk of pregnancy but without taking any contraceptive measures;
- ⑥Patients with apparent suicide attempt or suicidal behavior;
- ⑦ Any condition or medicines that may have an effect on biomarkers (within 1 week of the screening period or during whole trial period): long-term, regular use of NSAIDs, COX-2 inhibitors, immunosuppressant, steroids, interferon, chemotherapeutics, anticoagulants, malignancy, active autoimmune diseases, inflammatory bowel diseases, etc;
- ⑧Allergy history of PUFA;
- ⑨Intake of Fish oil more than 3g per day or eat fatty fish more than 3 times a week.

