2.4 Assessment

Following consent, patients met enrollment criteria to be in the study will be undergone assessments including:

- ① Demographic information, medical and psychiatric history and family history of mental illnesses at baseline;
- ②Labs: CBC, metabolic panel, liver panel and lipid panel (extra sample will be saved for biomarkers);

- ③Clinical symptom will be assessed by HAMD;
- ④Cognitive assessment by RBANS and STROOP;
- ⑤Side effect rated on UKU and Lab tests.

Almost all clinical assessments will be done at baseline, week 4, week 8, week 12, week 24 and week 48, except some items being done at baseline only (See table 1 for details).

For the lab work, in addition to routine clinical safety lab, some extra blood sample will be collected and stored for future epigenetic and bio-inflammatory biomarkers assay.

Table 1: Schedule of Clinical, Neurocognitive Assessment and Lab testing for Evaluation of fish oil add-on therapy in MDD

	Baseline	W04	W08	W12	W24	W 48
Inform consent	*					
Inclusion/exclusion screen	*					
Demographic & medical, mental illness history	*					
Physical exam	*	*	*	*	*	*
Lab test and blood sample stored	*	*		*	*	*
Randomization	*					
Study medication dispense	*	*	*	*		
HAMD, HAMA, CGI, BDI, SAS, RBANS, STROOP, ASEX, Somatic Self-rating Scale	*	*	*	*	*	*
CTQ, SSRS	*					
UKU		*	*	*	*	*
BMD	*				*	*
MRI	*				*	*

3 Overall Approach to Statistical Analysis

Data will be examined for obvious outliers, distribution irregularities, and range errors and processed accordingly. Prior to analyses, the validity of assumptions (e.g., about distributions) will be confirmed. Transformations will be made or a nonparametric procedure may be utilized as needed. Means, standard deviations, ranges or interquartile ranges, and rates of primary outcomes will be reported. Baseline demographics and characteristics will be compared among study groups using F-tests or chi-square tests

or nonparametric equivalents as needed. Baseline variables with significant group differences will be treated as potential confounder variables and will be statistically adjusted for in analyses. Unless stated otherwise, two-sided testing and a 5% level of significance are planned for all statistical tests.

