The primary outcome measures will be the clinical symptoms Changes in Hamilton Depression Scale HAMD 6 weeks at week 0, week 4, week 12, week 24 and week 48 among study groups. Secondary outcome measures the Changes in Clinical Global Impression (CGI), Hamilton Anxiety Scale (HAMA), Beck Depression Rating Scale (BDI) and Self-Rating Anxiety Scale (SAS) at week 0, week 4, week 12, week 24 and week 48. And time to relapse for the maintenance phase of the study among study groups.

For hypothesis: Subjects who are randomized to the fish oil will have reduced clinical symptoms and perform better in cognition and improve metabolic markers; inflammation markers than those who are randomized to placebos.

Analyses: After transformation (if necessary to insure the improvement is linear), the difference in the rate of HAMD improvement of fish oil group will be compared with that of the placebo group and the linear mixed effects models will be performed using subjects as the random effect (i.e. the drug-time interaction, with adjustment for baseline values). Secondary analyses will include using GLM to test if treatment arms show effect on CGI, HAMA, BDI, SAS, and other psychological variables. We will also evaluate possible cofounders as well as improvement of neurocognitive domains score and CGI.

4 Key investigator list

Principal Investigator (PI)

[name]. M.D.

Chief Clinical Professor

Mental Health Institute

Second Xiangya Hospital of Central South University

[name]

[contact]

E-mail: [contact], or [contact]

[name]. M.D. (Co-PI)

Department of Pharmacy Xiangya Hospital, Central South University

[name]

[contact]

E-mail: [contact]

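### The primary HAMD slope test names the patient as the random effect but states no random slope, within-patient covariance or robust standard error, so its two-sided 5% level is not assured if patients differ in true rate of change

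*Combined protocol and SAP*

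**What the plan says.** The primary analysis is described in one sentence of section 3, Overall Approach to Statistical Analysis. What is compared is a rate: "the difference in the rate of HAMD improvement of fish oil group will be compared with that of the placebo group". The model is given as "linear mixed effects models will be performed using subjects as the random effect (i.e. the drug-time interaction, with adjustment for baseline values". A linear trend is to be secured first: "After transformation (if necessary to insure the improvement is linear".

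The primary outcome text lists HAMD at "week 0, week 4, week 12, week 24 and week 48 among study groups". Table 1 in section 2.4 also schedules HAMD at week 8.

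The same section makes a general promise that "the validity of assumptions (e.g., about distributions) will be confirmed", and gives the remedy as "Transformations will be made or a nonparametric procedure may be utilized as needed". It adds that "two-sided testing and a 5% level of significance are planned for all statistical tests". The Brief Summary names SPSS as the software, without a procedure or options. No section gives a random slope, a residual covariance structure, a robust standard error or a degrees-of-freedom method.

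**The concern.** The hypothesis is about slopes. A random intercept lets patients differ in level but makes every patient in an arm share one true slope. If patients in fact improve at different rates, that variation belongs in the standard error of the between-arm slope difference. A random-intercept model treats it as visit-to-visit noise and spreads it over all the within-patient degrees of freedom. When the mean course is linear on the analysis scale, the reported standard error is then too small, the confidence interval too narrow and the primary p-value too small.

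The two safeguards in section 3 do not settle this. A transformation that makes the average trend linear does not make patients' slopes equal on the new scale. The assumption check gives distributions as its example, and its remedies do not specify the covariance of the mixed model.

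**Working it through.** **Inputs from the documents.** Two-sided 5% (section 3); 60 patients per arm (section 2.2: "Sixty subjects will be given fish oil and another 60 subjects given placebo (control group"); visit weeks from section 3 and Table 1.

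**Assumed inputs.** Residual SD s = 5 HAMD points. D, the between-patient SD of true change from week 0 to week 48, is 2.4, 4.8, 7.2 or 9.6 points. Time is raw weeks or log(week+1), the latter only as an example of a transformation. At first, data are complete and the mean course is linear on the scale used.

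**Formula.** Let m be the number of response visits, Sxx the sum of squared deviations of the visit times, and T the SD of true slopes (D/48 on raw weeks, D/ln 49 on the log scale). In balanced data the drug-time estimate is the difference in mean within-patient slopes, so a baseline covariate does not change it.

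- True variance is proportional to s² + T²·Sxx.
- The variance reported by a random-intercept fit is proportional to s² + T²·Sxx/(m−1).
- Actual level = 2·[1 − Φ(1.96/√ratio)], where ratio = true/reported. The number per arm cancels.

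**Reproducing the plan's 5%.** At D = 0 the ratio is 1 and the level is 5.0%.

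**One case in full.** Weeks 4, 12, 24, 48, raw weeks, D = 4.8: Sxx = 1104, T = 0.1, T²·Sxx = 11.04. True 25 + 11.04 = 36.04; reported 25 + 11.04/3 = 28.68; ratio 1.257; standard-error ratio 1.121; level 8.0%.

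**All cases (actual level, %).**

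| Response visits (weeks) | Time scale | Sxx | D = 2.4 | 4.8 | 7.2 | 9.6 |
|---|---|---|---|---|---|---|
| 4, 12, 24, 48 | raw | 1104.0 | 5.8 | 8.0 | 10.9 | 13.7 |
| 4, 12, 24, 48 | log | 2.838 | 5.3 | 6.3 | 7.7 | 9.5 |
| 4, 8, 12, 24, 48 | raw | 1260.8 | 6.1 | 9.0 | 12.9 | 16.6 |
| 4, 8, 12, 24, 48 | log | 3.150 | 5.4 | 6.6 | 8.5 | 10.7 |
| 0, 4, 12, 24, 48 | raw | 1491.2 | 6.3 | 9.6 | 13.9 | 17.8 |
| 0, 4, 12, 24, 48 | log | 9.206 | 6.2 | 9.4 | 13.5 | 17.4 |
| 0, 4, 8, 12, 24, 48 | raw | 1568.0 | 6.4 | 10.3 | 15.3 | 20.0 |
| 0, 4, 8, 12, 24, 48 | log | 9.209 | 6.3 | 9.8 | 14.5 | 19.0 |

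The first four rows match the plan's adjustment for baseline most directly. The last four apply only if week 0 is also a response. In the first two rows the correct standard error exceeds the reported one by 3–32% (raw) or 1–17% (log), and the level stays at or below 6% while D/s is at most 0.53 (raw) or 0.85 (log).

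**Simulation check.** With 60 per arm, complete data and 20,000 trials per cell, the random-intercept test at weeks 4, 12, 24, 48 and D = 0, 2.4, 4.8, 7.2, 9.6 rejected in 5.2, 6.0, 8.0, 10.8, 13.9% (raw) and 5.1, 5.6, 6.2, 7.4, 9.7% (log). Comparing per-patient slopes rejected in 4.6–5.4% across these and the cells with week 0 as a response (weeks 0, 4, 12, 24, 48). With an assumed 25% random dropout and 4,000 trials per cell, REML random-intercept fits at D = 0, 4.8, 9.6 rejected in 5.7, 8.4, 14.2% (raw) and 5.3, 6.6, 9.8% (log). Patient-clustered robust standard errors on the dropout fits, with and without week 0 as a response, gave 4.6–5.9%.

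**Relaxing linearity.** Suppose both arms share a curved course that is fitted as a straight line in raw weeks. Let L be the sum of squared departures of that course from its best straight line over the visits. L cancels from the arm contrast but inflates the residual, so the reported variance becomes s² + (T²·Sxx + L)/(m−1). Assume an exponential fall of 10–15 points with a time constant of 6–12 weeks.

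- Weeks 4, 12, 24, 48: about 3–4% at D = 0, 4–5% at D = 2.4 and 6–7% at D = 4.8.
- Weeks 0, 4, 12, 24, 48: 1.1–3.6% at D = 0, 1.7–4.7% at D = 2.4, 3.6–7.8% at D = 4.8 and 10.8–16.0% at D = 9.6.

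For example, a 10-point fall with a 12-week constant gives L = 5.72 on the first set; at D = 0 the ratio is 25/(25 + 5.72/3) = 0.929 and the level 4.2%.

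**The case against.** The plan does not say intercept, nor that it is the only random term, and the parenthesis after the random effect mentions time. If the analyst fits a patient-level slope, the problem disappears. This stands: the random-intercept reading is an inference. It is still the ordinary reading of the phrase, and a plan that permits either model leaves the primary p-value open to a later choice.

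A reader might infer that the p-value is too small whenever slopes differ. The documents do not support that. It needs a linear mean course, and with a shared curve the error can run the other way when slope variation is small. Capsules stop at 24 weeks and follow-up runs to week 48, so curvature is plausible. If the planned transformation does achieve linearity, this part of the objection lapses, but the raw-week figures then apply only where no transformation was needed.

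A reader might also take the levels near 20% as the headline. They require week 0 as a response, whereas the text speaks of adjusting for baseline. D and s are assumptions throughout, and the plan does not say whether time or HAMD would be transformed. If HAMD is transformed, D in points has no direct meaning.

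The promise to confirm assumptions is not limited to distributions. It is still generic and names no covariance remedy.

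**Conclusion.** The point holds as a conditional one. On the ordinary random-intercept reading, the standard error of the primary slope contrast is not valid if patients differ in true slope, so the 5% level is not assured.

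With a linear mean course, s = 5, D = 2.4–9.6 and baseline as covariate, the level is 5.8–13.7% (raw weeks) or 5.3–9.5% (log) on the visits in section 3. It is 6.1–16.6% or 5.4–10.7% if the scheduled week 8 is added, and about 6–20% only if week 0 is also a response. With equal slopes and a linear course it is 5%. With a shared curve fitted as a line it can be below 5%. Direction and size therefore cannot be fixed from the documents, and they do not show that a wrong model has been chosen. The change is worth making because the primary test should not rest on an unstated assumption of equal slopes. Confidence is medium.

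**What to change.** In the planned slope model of section 3, specify a random intercept and a random slope for time per patient, on the analysis time scale, with Satterthwaite or Kenward-Roger degrees of freedom. Base the drug-time test on patient-clustered robust standard errors, because a random slope alone need not correct for lack of fit to a shared curve. If the model does not converge, compare per-patient slopes between arms. State in the same place which visits enter and whether week 0 is a covariate or a response, since the size of the problem depends on both; week 8 needs reconciling between section 3 and Table 1.

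The cost is about two sentences and one extra random term, with no new data. Intervals will be somewhat wider if slopes vary, and there is a small convergence risk, which the named fallback covers.

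### CGI, HAMA, BDI and SAS follow the HAMD visit schedule but are assigned a GLM of unstated form; a baseline-adjusted mixed model should replace it, with a gain that depends on which GLM is meant

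*Combined protocol and SAP*

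**What the plan says.** Section 3, in the paragraph on analyses, compares the rate of HAMD improvement between arms and says that "the linear mixed effects models will be performed using subjects as the random effect (i.e. the drug-time interaction, with adjustment for baseline values"). The next sentence turns to the remaining scales: "Secondary analyses will include using GLM to test if treatment arms show effect on CGI, HAMA, BDI, SAS, and other psychological variables". It does not say whether GLM means a univariate, repeated-measures or generalized linear model, which visits enter, or how correlation within a patient is handled.

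Section 2.4 says "Almost all clinical assessments will be done at baseline, week 4, week 8, week 12, week 24 and week 48", with some baseline-only exceptions. One row of Table 1, "HAMD, HAMA, CGI, BDI, SAS, RBANS, STROOP, ASEX, Somatic Self-rating Scale", is marked at all six visits. Section 3 names only five for the secondary outcomes, ending with "Self-Rating Anxiety Scale (SAS) at week 0, week 4, week 12, week 24 and week 48", so week 8 is absent there.

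The documents contain no missing-data rule, no definition of an analysis population, and no reason for treating HAMD and the other scales differently. The Brief Summary names SPSS as the software for the whole trial.

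**The concern.** The data have the same structure for all these scales: one baseline and up to five later values per patient. A likelihood-based mixed model uses every available post-baseline value. A GLM, in either of its usual forms here, does not.

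- **Repeated-measures GLM.** Each patient is one row holding all visits, and a patient with any empty cell is dropped. A patient who finished 24 weeks of capsules but missed week 48, which falls 24 weeks after capsules end, would contribute nothing to the week-24 result on HAMA or BDI. HAMD and the supporting scales would rest on different patients, and completers may not be representative.
- **GLM at each visit.** Each analysis uses whoever attended that visit. Each scale gives four or five tests at the 5% level, with no time point marked as the main one. Earlier post-baseline scores are ignored, although they may predict who drops out.

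The Brief Summary lists HAMA, BDI and SAS as primary outcome measures while Section 3 calls them secondary, so the GLM may fall on outcomes called primary elsewhere.

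**Working it through.** The documents give no retention rate, missed-visit rate, SD, correlation or power figure, so there is no stated figure to reproduce.

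**From the documents.** 120 patients, 60 per arm; five post-baseline visits in Table 1 (weeks 4, 8, 12, 24, 48) or four in Section 3 (week 8 left out).

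**Assumed.** Retention to week 48 of 80% (65% as a worse case). Patients still in the trial miss 5% of visits at random (0% as a milder case). Correlation between two visits is 0.4 + 0.3·exp(−lag/12), lag in weeks. SD is 7, which cancels from the ratios. Dropout timing takes three shapes: exponential in time, linear in time, or equal per visit.

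**Step 1: share of patients with every visit.** Share = retention × (1 − miss rate)^visits.

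- Five visits: 0.80 × 0.95^5 = 0.80 × 0.774 = 0.619, about 74 of 120.
- Four visits: 0.80 × 0.95^4 = 0.80 × 0.815 = 0.652, about 78 of 120.
- 65% retained, five visits: 0.65 × 0.774 = 0.503.

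**Step 2: variance of the arm difference.** Let C be the covariance of the post-baseline scores after conditioning on baseline. The mixed model's information is the sum, over patterns of observed visits, of the pattern's probability times the inverse of the matching block of C. Its week-24 variance is the week-24 diagonal element of the inverse of that sum. For complete cases the variance is C(24,24) divided by the share complete. For a per-visit GLM it is C(24,24) divided by the share seen at week 24. The comparator treats visit as categorical with unstructured covariance. Results with five visits, as ranges over the dropout shapes:

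| Retained / missed | Complete | Complete-case ÷ mixed, week 24 | Complete-case ÷ mixed, on-treatment average | Per-visit ÷ mixed, week 24 |
|---|---|---|---|---|
| 80% / 5% | 62% | 1.32–1.41 | 1.45–1.53 | 1.02–1.03 |
| 65% / 5% | 50% | 1.39–1.61 | 1.65–1.82 | 1.03–1.04 |
| 80% / 0% | 80% | 1.06–1.14 | 1.15–1.21 | 1.01–1.02 |

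With Section 3's four post-baseline visits, 80% retained and 5% missed, the week-24 complete-case ratio is 1.26–1.34.

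**Step 3: check of the first row.** The complete-case ratio equals (share seen at week 24 ÷ share complete) × the per-visit ratio.

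- Linear dropout: share seen = (1 − 0.20 × 24/48) × 0.95 = 0.855; 0.855 / 0.619 = 1.381; × 1.022 = 1.41.
- Equal per visit: share seen = 0.80^(4/5) × 0.95 = 0.795; 0.795 / 0.619 = 1.284; × 1.025 = 1.32.

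So nearly all the loss under complete-case analysis comes from discarding patients who did attend week 24. The mixed model's borrowing from other visits adds only 2–3% here.

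**Step 4: number of tests under a per-visit GLM.** Four named scales × five post-baseline visits = 20 tests (4 × 4 = 16 on Section 3's list), none given priority.

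**The case against.** The strongest reply is that the documents never say repeated-measures. A reader might infer from the naming of SPSS that every patient with one missed visit will be dropped. That does not follow: SPSS is named for the whole trial, the HAMD mixed model included, so it does not identify the form of GLM. A reader might also infer that the loss is equally serious whichever form is meant. The table shows otherwise: a baseline-adjusted per-visit GLM is almost as precise as the mixed model at week 24. Both points stand.

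Nor can it be said that the model needed is already in the plan. Section 3 compares a rate of improvement, transformed if needed to make it linear, with subject as the random effect. That reads as a linear-slope model, not the categorical-visit model used as comparator above. Copying it to the other scales would be a different change.

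The power cost can also be small. In a simulation of the averaged effect (assumed correlation 0.6, effect 0.5 SD at every post-baseline visit, data missing completely at random), complete-case power was 99.0% against 99.7% for a mixed model at 5% missed per visit, and 95.3% against 99.3% at 10%. Power there is close to its ceiling, which hides part of the loss. Section 3 labels these analyses secondary, and its wording does not make GLM the only method. The HAMD analysis is untouched.

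None of this supplies a reason to prefer GLM. Under either form the mixed model is at least as precise in these calculations, and it is better protected when dropout depends on observed scores.

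**Conclusion.** The concern holds in conditional form, as a change that should be made rather than one that threatens the trial. It is certain that scales on one visit schedule get different methods, that the GLM's form is unstated, and that no missing-data rule exists. The size depends on the form. For repeated-measures GLM, about 62–65% of patients are analysed and week-24 variance is about 1.3 to 1.4 times the mixed model's under 80% retention and 5% sporadic misses. The variance ratio falls to about 1.06–1.14 with no sporadic misses. For per-visit GLM the loss is about 1–4%, and the case rests on unprioritised tests and on dropout related to earlier post-baseline scores, which was not sized. Retention, missed visits, correlation and dropout timing are all assumptions, and the variance ratios treat missingness as random.

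**What to change.** In Section 3, replace GLM for CGI-S, HAMA, BDI and SAS with a likelihood-based mixed model on all available post-baseline visits. Include arm, visit, arm-by-visit and the scale's own baseline, and name one week-24 contrast. Apply it to RBANS and STROOP as well if they are meant by the other psychological variables, and say whether they are. Use the same model form for HAMD or state why it differs. Reconcile Table 1 with Section 3 on whether week 8 is analysed. Analyse CGI-I by its level, without a baseline covariate, because it already measures change.

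The cost is SAP wording and a little programming. Visits, sample size and trial conduct do not change.
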